5.4.2 Mean Score of FACT/GOG NTX1-4

Mean score of the first 4 items of the FACT/GOG-NTX-13 (i.e. FACT/GOG-NTX-4), at 9 months after the first dose of IMP.

Baseline is defined as the time of administration of the first dose of IMP (Day 1, Cycle 1).

Analysis of Covariance. Mean score of FACT/GOG NTX1-4 will be analysed by Analysis of Covariance (ANCOVA) using the baseline value as a continuous covariate and study (POLAR-A / POLAR-M), region (Asia / non-Asia) and treatment as factors. Least square means and its corresponding 95% confidence intervals will be presented.

Data presentations

- Table: ANCOVA analysis - Number of patients (N), Point Estimate (LSM), 95% CI and P-value by treatment group/treatment comparison (PledOx 5 µmol/kg vs Placebo).
- Table: descriptive statistics of observed values by treatment and total for each treatment cycle.
- Table: descriptive statistics of change from baseline by treatment and total for each treatment cycle.
- Figure: shift plot of baseline vs 9-month assessment visit.

All observed values of the Mean Score of FACT/GOG NTX1-4 will also be listed by patient.

5.4.3 Mean Score of FACT/GOG NTX1-13

Endpoint. Mean score of the 13 items of the FACT/GOG-NTX-13, at 9 months after the first dose of IMP.

Baseline. Defined as the time of administration of the first dose of IMP (Day 1, Cycle 1).

Analysis of Covariance. Mean score of FACT/GOG-NTX-13 will be analysed by Analysis of Covariance (ANCOVA) using the baseline value as a continuous covariate and study (POLAR-A / POLAR-M), region (Asia / non-Asia) and treatment as factors. Least square means and its corresponding 95% confidence intervals will be presented.

Data presentations

- Table: ANCOVA analysis - Number of patients (N), Point Estimate (LSM), 95% CI and P-value by treatment group/treatment comparison (PledOx 5 µmol/kg vs Placebo).
- Table: descriptive statistics of observed values by treatment and total for each treatment cycle.
- Table: descriptive statistics of change from baseline by treatment and total for each treatment cycle.
- Figure: shift plot of baseline vs 9-month assessment visit.

All observed values of the Mean Score of FACT/GOG NTX1-13 will also be listed by patient.

5.4.4 Cumulative Dose of 5-FU

Endpoint. Mean cumulative dose of 5-FU (IV Bolus/IV Continued Infusion) administered per patient during mFOLFOX6 chemotherapy, 9 months after the first dose of IMP. Summary statistics of 5-FU related variables are presented in Section 4.4.3.

In case the patient receives more than 12 cycles of 5-FU, that will also be accounted for when deriving the cumulative dose.

Analysis of Variance. Mean cumulative dose of 5-FU will be analysed by Analysis of Variance (ANOVA) using study (POLAR-A / POLAR-M), region (Asia / non-Asia) and treatment as factors. Least square means and its corresponding 95% confidence intervals will be presented. In case the distribution of the endpoint deviates from normality the endpoint will be log-transformed and the inference will be based on the geometric mean, ratio of geometrics means and corresponding 95% CIs.

Data presentation

- Table: ANOVA analysis - Number of patients (N), Point Estimate (LSM), 95% CI and P-value by treatment group/treatment comparison (PledOx 5 µmol/kg vs Placebo).

All observed values of mean cumulative dose of 5-FU will also be listed by patient.

5.4.5 Pharmacokinetics

The PK population (POLAR-M only) includes a subset of patients at pre-selected sites in all participating regions, where blood samples will be collected for pharmacokinetic assessments. Blood samples to measure plasma concentrations of PledOx will be taken pre-dose, 6 min post-dose, 15 min post-dose, 30 min post-dose, 60 min post-dose, and 240 min post-dose at treatment visit 1, 4 and 8. In addition, the PK parameters C_{max} , t_{max} , AUC_{0-last} of PledOx will be derived.

Values below LLOQ will be set to LLOQ/2.

Data presentations

- Table: descriptive statistics of plasma concentrations of PlexOx by visit and time point.
- Table: descriptive statistics of pharmacokinetic parameters of PlexOx.
- Graph: mean plasma concentrations of PledOx by time for each cycle.

The analyses will be done on the PK population. All observed values of plasma concentrations and PK parameters of PledOx will also be listed by patient.

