6.2 Laboratory Evaluation

Laboratory testing will be performed at each visit just before IMP administration. Local laboratories will be used to analyse the samples, and the local units will be standardised using SI-units for all reporting of laboratory tests.

Hematology

Hematology test will be performed at screening, treatment visit 1-12, End of Treatment visit, and assessment visit 1-8. The following hematology tests will be performed:

Hematology Test	SI-unit
Hemoglobin	g/L
Leukocytes	10 ⁹ /L
Neutrophils (Differential)	%
Lymphocytes (Differential)	%
Monocytes (Differential)	%
Eosinophils (Differential)	%
Basophils (Differential)	%
Neutrophils (absolute)	10 ⁹ /L
Erythrocytes (absolute)	10 ¹² /L
Platelet	10 ⁹ /L

Biochemistry

Biochemistry test will be performed at screening, treatment visit 1, 4, 8, 12 and End of Treatment visit. The following biochemistry tests will be performed:

Biochemistry Test	SI-unit
Alkaline Phosphatase (ALP)	IU/L
Total Bilirubin	umol/L
Alanine Aminotransferase (ALT)	IU/L
Aspartate Aminotransferase (AST)	IU/L
Creatinine	umol/L
Albumin	g/L

Baseline

For hematology and biochemistry laboratory tests baseline is defined as the sample taken prior to first dose of IMP. In case of missing, the screening measurement will be used instead.

Derived variables

- For all laboratory tests change from baseline will derived for all post-baseline measurements.
- A laboratory value marked as LLOQ or having a registered value <LLOQ will be imputed by LLOQ/2. In case >50% of the values at a timepoint are <LLOQ the mean will be set to LLOQ.

Values outside normal ranges

Laboratory values outside the normal ranges will be flagged in the laboratory report. For each flagged value the Investigator should mark the value as “Clinically Significant” (CS) or “Not Clinically Significant” (NCS).

Data presentations

- Table: for each laboratory test, descriptive statistics of observed values by treatment group, total and by treatment/assessment visit.
- Table: for each laboratory test, descriptive statistics of change from baseline by treatment group, total and by treatment/assessment visit.
- Figure: for each laboratory test, scatterplot (using jitter) of observed values by treatment group and treatment/assessment visit.
- Table: for each laboratory test, number and percentage of patients with clinically significant values outside normal ranges by treatment group and treatment/assessment visit.

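### The below-LLOQ rules in SAP 5.4.5 and 6.2 need limits: LLOQ/2 is not kept out of AUC0-last, and the laboratory mean is set to a constant that contradicts its own imputation

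*SAP*

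**What the plan says.** **PK (SAP 5.4.5, POLAR-M subset).** Plasma is sampled "pre-dose, 6 min post-dose, 15 min post-dose, 30 min post-dose, 60 min post-dose, and 240 min post-dose" at treatment visits 1, 4 and 8. The section states that Cmax, tmax and AUC0-last "of PledOx will be derived". The next line is its only rule for low values: "Values below LLOQ will be set to LLOQ/2". It makes no exception for pre-dose samples or for samples after the last quantifiable one. It does not separate the concentration tables from the parameter derivation.

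**Laboratory (SAP 6.2).** One bullet carries two rules. The first is "A laboratory value marked as LLOQ or having a registered value <LLOQ will be imputed by LLOQ/2". The second is "In case >50% of the values at a timepoint are <LLOQ the mean will be set to LLOQ". Observed values and change from baseline are both tabulated with descriptive statistics. Local laboratories analyse the samples; their units are standardised, but no common LLOQ is mentioned.

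**The concern.** By its usual meaning, AUC0-last ends at the last measurable concentration. If every low value is first replaced by a positive number, no sample counts as unmeasurable and the parameter loses that meaning. The sampling scheme makes this matter, because the final interval (60 to 240 min) covers 180 of the 240 minutes. A patient measurable at 60 min but not at 240 min gets a long final segment ending on an imputed point. Two programmers working from this text could produce different AUCs.

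In the laboratory section, the two halves of the bullet cannot both describe the same data. The imputation makes most of the averaged values LLOQ/2, and the mean is then overwritten with LLOQ. A table can therefore show a mean that its own minimum, median and maximum rule out.

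**Working it through.** The SAP states no figure on this point to reproduce. It also gives no LLOQ, concentrations or half-life, so the PK numbers below illustrate assumed profiles only.

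**1. PK.** The times 0, 6, 15, 30, 60 and 240 min are from SAP 5.4.5. Assumptions: LLOQ = 1, C(6) = 20, C(t) = 20·exp(−k(t−6)) with k = ln 2 / half-life, true pre-dose value zero, linear trapezoid.

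Worked case, half-life 30 min:
- Concentrations at 6, 15, 30, 60 and 240 min are 20, 16.2, 11.5, 5.74 and 0.09. The last one is below LLOQ.
- AUC to the last quantifiable sample (60 min): 60.0 + 163.1 + 208.0 + 258.5 = 690.
- Literal rule: the pre-dose value of 0.5 adds 0.5 × 6/2 = 1.5. The last segment adds (5.74 + 0.5)/2 × 180 = 562. The total is 1253.
- Ratio: 1253/690 = 1.82.

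Same calculation for other half-lives (LLOQ·min):

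| Half-life (min) | Last quantifiable sample (min) | AUC to that sample | AUC under literal rule | Ratio | Total area under assumed curve |
|---|---|---|---|---|---|
| 10 | 30 | 307 | 463 | 1.51 | 349 |
| 20 | 60 | 568 | 891 | 1.57 | 637 |
| 30 | 60 | 690 | 1253 | 1.82 | 926 |
| 45 | 60 | 800 | 1630 | 2.04 | 1358 |

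At a half-life of 60 min the 240-min sample is quantifiable. Only the 1.5 LLOQ·min from the pre-dose value is added, so the ratio is about 1.00. When C(6) is varied from 10 to 1000 x LLOQ and the half-life from 10 to 60 min, the ratio is 1.12 to 2.22 if the 240-min sample is below LLOQ and about 1.00 if it is not. A profile with every sample below LLOQ would receive 0.5 × 240 = 120 LLOQ·min.

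**2. What the ratio contains.** The two AUCs cover different spans (0–240 min against 0–30 or 0–60 min). To isolate the imputation, compare the literal rule with a linear trapezoid over 0–240 min that uses the assumed true concentrations: 463/414, 891/845, 1253/1215 and 1630/1633. The imputation alone changes the AUC by +12%, +5%, +3% and −0.2%.

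**3. Laboratory.** Let f be the share below LLOQ and a the mean of the quantifiable values, in LLOQ units (a ≥ 1). The mean after imputation is M = 0.5f + (1 − f)a. The rule reports 1.0 whenever f > 0.5.
- f = 1: M = 0.5, reported as 1.0, with minimum, median and maximum all 0.5.
- f = 0.51, a = 3: M = 0.255 + 1.47 = 1.73, reported as 1.0 (too low).
- f = 0.80, a = 2: M = 0.40 + 0.40 = 0.80, reported as 1.0 (too high).
- M equals 1.0 only if a = (1 − 0.5f)/(1 − f), which is 1.52, 1.75, 3.0 and 5.5 at f = 51%, 60%, 80% and 90%.

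**The case against.** - **The order of steps is not stated.** SAP 5.4.5 does not say that substitution precedes the AUC derivation. The rule stands between the parameter list and the data presentations, the first of which is a concentration table, so it can be read as a rule for that table. This stands: the literal reading is an inference. It also shows why the rule should be limited in words.
- **A reader might infer that LLOQ/2 overstates the true AUC by 20–40%.** The literal-rule values do exceed the total area by that much in these profiles. Step 2 shows, however, that imputation accounts for only −0.2% to +12%, and the rest comes from the assumed linear trapezoid across the 180-minute gap. Truncating at the last quantifiable sample also misses: it falls 12%, 11%, 25% and 41% short of the total. At 45 min the literal rule (+20%) is closer. The finding is that the reported quantity is not the one named, not that it is always less accurate.
- **A reader might infer that the laboratory mean always exceeds every value averaged.** That is true only when all values are below LLOQ. Otherwise at least one value is at or above LLOQ.
- **A reader might infer a false difference between arms, for example at 49% and 51% below LLOQ.** The 50% criterion is stated per timepoint, not per arm, and SAP 6.2 plans no test. The SAP does not support the claim that a treatment difference would be created or hidden.
- **No affected sample is shown to exist.** This also stands. The share of values below LLOQ is unknown for both PK and laboratory tests, and individual values are listed by patient.

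**Conclusion.** The point holds as a minor defect in two stated rules. In 5.4.5 the substitution has no limit, and followed literally it turns AUC0-last into an AUC to 240 min for every fully sampled profile. For the assumed profiles with C(6) at 20 x LLOQ and a 240-min value below LLOQ, the result is 1.51 to 2.04 times the AUC to the last quantifiable sample. That size depends on the assumed curve, level and trapezoid, and it combines longer span with imputation. In 6.2 the contradiction needs no assumption: the bullet imputes one value and reports a mean based on another. The error is a factor of two when all values are below LLOQ and can go in either direction otherwise. PK is exploratory and descriptive, and the laboratory tables are descriptive safety output. The primary analysis does not depend on either.

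**What to change.** **SAP 5.4.5.** State that LLOQ/2 applies only to the concentration summaries, and show the number below LLOQ at each time point. Derive AUC0-last to the last quantifiable sample. For that derivation, set values below LLOQ before the first dose to zero and exclude values below LLOQ after the last quantifiable sample. Say also how a pre-dose value below LLOQ at treatment visits 4 and 8 is handled.

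**SAP 6.2.** Delete the rule that sets the mean to LLOQ. Where more than 50% of values at a timepoint are below LLOQ, report the median and n (%) below LLOQ, with no mean and no mean change. The median then falls among the imputed values, so label it as below LLOQ. This also avoids having to choose one LLOQ across local laboratories.

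**Cost.** A few lines of SAP text and a programming rule for each section. Some mean cells will be blank. Other conventions would also serve, provided one is fixed before unblinding.

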5.4.6 ECG QT/QTc

Mean QT/QTc interval using a 12-lead ECG at all measured time points.

The ECG variables is measured pre- and post-dose at cycle 1, 4 and 8, and at the End of Treatment visit. Baseline is defined as the time of administration of the first dose of IMP (Day 1, Cycle 1).

ECG variables:

- ECG Mean heart rate
- Interpretation
- PR interval
- QRS duration
- QT interval
- QTcB interval
- QTcF interval
- RR interval

Data presentations

- Table: number (%) of patients with abnormal ECG by visit and time point.
- Table: descriptive statistics of each continuous ECG variable by visit and time point.

The ECG analyses will be done on the PK population. All observed values of the ECG variables will also be listed by patient.

5.4.7 EQ-5D-5L and Health VAS Score

Mean EQ-5D-5L health index and Health VAS score at 9 and 12 months after the first dose of IMP.

EQ-5D-5L Health Index. The EQ-5D-5L is a standardized instrument for use as a measure of health outcome. It is often referred to as a Quality of Life (QoL) questionnaire. The EQ-5D-5L comprises 5 dimensions of health:

- Mobility
- Ability to self-care
- Ability to undertake usual activities
- Pain and discomfort
- Anxiety and depression

There are 5 options (levels, ordinal scale) under each dimension.

Endpoint. Mean health index is defined as the mean value of the 5 dimensions of the EQ-5D-5L questionnaire and will be analysed 9 and 12 months after the first dose of IMP, respectively.

Baseline. Baseline is defined as the time of administration of the first dose of IMP (Day 1, Cycle 1).

Analysis of Covariance. Mean health index will be analysed by Analysis of Covariance (ANCOVA) using the baseline value as a continuous covariate and study (POLAR-A / POLAR-M), region (Asia / non-Asia) and treatment as factors. Least square means and its corresponding 95% confidence intervals will be presented.

Data presentations

- Table: ANCOVA analysis - Number of patients (N), Point Estimate (LSM), 95% CI and P-value by treatment group/treatment comparison (PledOx 5 µmol/kg vs Placebo).
- Table: descriptive statistics of observed values by treatment and total
- Table: descriptive statistics of change from baseline by treatment and total

All observed values of Mean Health Index and Mean VAS Score will also be listed by patient.

Endpoint. Health VAS Score, the patient health status is also measured on a Visual Analogue Scale (VAS) ranging from 0 to 100, where 100 means best health and 0 worst health.

Baseline. Baseline is defined as the time of administration of the first dose of IMP (Day 1, Cycle 1).

Analysis of Covariance. Health VAS score will be analysed by Analysis of Covariance (ANCOVA) using the baseline value as a continuous covariate and study (POLAR-A / POLAR-M), region (Asia / non-Asia) and treatment as factors. Least square means and its corresponding 95% confidence intervals will be presented.

Data presentations

- Table: ANCOVA analysis - Number of patients (N), Point Estimate (LSM), 95% CI and P-value by treatment group/treatment comparison (PledOx 5 µmol/kg vs Placebo).
- Table: descriptive statistics of observed values by treatment and total
- Table: descriptive statistics of change from baseline by treatment and total

All observed values of Health VAS Score will also be listed by patient.

Endpoint. Number and percentage of patients by level of severity of the 5 dimensions of the EQ-5D-5L questionnaire.

Baseline. Baseline is defined as the time of administration of the first dose of IMP (Day 1, Cycle 1).

Data presentations

- Table: Number and percentage (%) of patients by level of severity of the 5 dimensions of the EQ-5D-5L questionnaire by treatment, total and visit

All observed values of the level of severity of the 5 dimensions of the EQ-5D-5L questionnaire will also be listed by patient.

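### SAP section 5.4.7 gives the name 'health index' to an unweighted mean of five ordinal EQ-5D-5L levels, with no coding or direction stated, so a treatment difference could be read the wrong way round

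*SAP*

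**What the plan says.** The endpoint in SAP section 5.4.7 is "Mean EQ-5D-5L health index and Health VAS score at 9 and 12 months after the first dose of IMP". The section describes the instrument in two steps: "The EQ-5D-5L comprises 5 dimensions of health", and "There are 5 options (levels, ordinal scale) under each dimension". It then fixes the derivation: "Mean health index is defined as the mean value of the 5 dimensions of the EQ-5D-5L questionnaire".

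The planned inference is "Mean health index will be analysed by Analysis of Covariance (ANCOVA) using the baseline value as a continuous covariate", with study, region and treatment as factors. The output is least-squares means, 95% confidence intervals and a p-value for PledOx 5 µmol/kg against placebo.

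Two other EQ-5D-5L outputs stand beside it. The Health VAS has its own ANCOVA, on a scale "ranging from 0 to 100, where 100 means best health and 0 worst health". There is also a descriptive table: "Number and percentage of patients by level of severity of the 5 dimensions of the EQ-5D-5L questionnaire".

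The SAP names no value set, dimension weights, numeric coding of the levels or direction for the index. Section 2.5 drops a mean health index based on the FACT/GOG, but that is a different instrument, and no change is listed for the EQ-5D-5L. The definition in section 5.4.7 therefore governs.

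**The concern.** There are two linked problems.

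**Name and content do not match.** A plain mean of level codes treats every step between adjacent levels as equal and every dimension as equally important. The SAP calls the levels ordinal and gives no reason for either assumption. For the FACT/GOG item averages in sections 5.4.2 and 5.4.3 the SAP uses the neutral term 'mean score'. Only here does an unweighted average of items carry the name 'health index', which invites readers to take it as a preference-weighted value.

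**The direction is open.** The section describes the levels as levels of severity. If the codes rise with severity, the 'health index' rises as health falls, while the VAS is anchored so that "where 100 means best health and 0 worst health". Two adjacent ANCOVA tables for the same objective would then run in opposite directions, with only one direction stated. For the primary endpoint the SAP is explicit: section 3.2 says a rate ratio below 1 favours PledOx. Section 5.4.7 has no such sentence for the index.

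At stake is how one exploratory quality-of-life result is read in the study reports: what the number measures, and which arm a difference favours.

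**Working it through.** The SAP gives no sample-size, power or effect figure for this endpoint, so there is no stated figure to reproduce. The check applies the SAP's definition to the health states that the instrument can record.

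**Inputs.** Five dimensions with five ordinal levels each, and the index as their mean (all section 5.4.7). Assumption: levels are coded 1 (least severe) to 5 (most severe). Coding 0 to 4 would lower every score by 1 and change no comparison. Profiles below follow the SAP's order: mobility, self-care, usual activities, pain, anxiety.

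**Formula.** Index = (sum of the five level codes) / 5.

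1. *Equal weights.* One level up in any dimension, from any starting level, moves the index by 1/5 = 0.2. Moving one dimension from level 1 to level 5 moves it by (5 − 1)/5 = 0.8. Moving four dimensions from level 1 to level 2 also moves it by 4 × (2 − 1)/5 = 0.8.

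2. *Different states, same score.* Profile 1-1-1-5-1 gives (1 + 1 + 1 + 5 + 1)/5 = 9/5 = 1.8. Profile 2-2-2-1-2 gives (2 + 2 + 2 + 1 + 2)/5 = 9/5 = 1.8. Over all 5^5 = 3125 states, the index takes 21 values (1.0 to 5.0 in steps of 0.2). The value 1.8 covers 70 states, of which 5 have one dimension at the worst level and 5 have no dimension above level 2. Ties of this kind are normal for any summary score and are not in themselves the fault.

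3. *The ranking depends on the coding.* An ordinal scale fixes only the order of the levels, so any increasing set of codes is equally admissible. Compare two profiles under codes 1, 2, 3, 4, 5 and under the illustrative increasing codes 0, 1, 2, 6, 10:

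| Profile | Codes 1, 2, 3, 4, 5 | Codes 0, 1, 2, 6, 10 |
|---|---|---|
| 4-1-1-1-1 | (4 + 4 × 1)/5 = 1.6 | (6 + 4 × 0)/5 = 1.2 |
| 2-2-2-2-1 | (4 × 2 + 1)/5 = 1.8 | (4 × 1 + 0)/5 = 0.8 |

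The first profile scores lower under one coding and higher under the other. Which state counts as worse is decided by the unstated codes and the equal-step assumption, not by anything in the SAP.

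4. *Direction.* With severity coding the best state scores 5/5 = 1.0 and the worst 25/5 = 5.0. The VAS runs from 100 (best) to 0 (worst). If the codes were instead reversed (6 minus level), the index would become 6 minus the mean, so a treatment difference of −0.2 would become +0.2. The SAP's text permits both, so the sign of the ANCOVA contrast cannot be read as benefit or harm from the SAP alone.

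**The case against.** The strongest reply is that little depends on this score. It is exploratory, outside the formal testing procedure in section 3, and one of three EQ-5D-5L outputs. The per-dimension severity table separates the two profiles that tie at 1.8, because the worst level of pain appears in the pain rows. The level data are listed by patient, so another score could be derived later. All of this stands and limits the size of the point.

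A second reply is that averaging ordinal items is common practice, also in this SAP: sections 5.4.2 and 5.4.3 analyse item means, and the cold-sensitivity, vibration and pain scales, all described as ordinal, go into ANCOVA. This also stands. Equal weighting and ties alone would not single out the EQ-5D-5L; what is specific here is the name 'health index' together with an unstated direction. The SAP nowhere says that a value set is required, and the point does not need it to: the score as defined carries no weights, whatever it is called.

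Several stronger readings are tempting, and the document does not support them:

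- *That the health-economic objective is undermined.* Section 5.4.11 plans summary statistics of resource use, patient impact and societal costs. It plans no utility or cost-utility step and does not use this index.
- *That the quality-of-life objective rests on this score.* The VAS analysis and the severity table serve the same objective.
- *That a positive difference means harm.* That follows only under increasing-severity coding, which the SAP suggests but does not state.
- *That equal weighting dilutes a neuropathy effect.* The SAP gives neither a source nor a figure for which dimensions neuropathy moves.

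**Conclusion.** The point holds in limited form. Section 5.4.7 sets an explicit rule that yields an unweighted average of ordinal severity levels, calls it a health index and attaches a p-value at two time points. It is not a preference-weighted index, and its direction is undefined. Under increasing-severity coding it runs opposite to the VAS beside it, so a treatment difference could be misread.

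That the score weights dimensions and steps equally follows from the definition under any equally spaced coding. The scores shown assume codes 1 to 5. The reversal against the VAS assumes that codes rise with severity. No corrected estimate can be given, because the SAP supplies neither a value set nor EQ-5D-5L data.

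The impact is confined to this one exploratory endpoint at 9 and 12 months. It is worth correcting because the correction is simple and the result would otherwise be reported under a misleading name.

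**What to change.** Amend section 5.4.7 before unblinding, in one of two ways:

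- **Derive an index.** Compute it from the five-dimension profile with one named published value set (country and version) applied to all patients in both studies. State that higher is better and run the planned ANCOVA on it.
- **Keep the mean.** Rename it 'mean level score', state the level coding (for example 1 to 5 by increasing severity) and that higher is worse, and do not report it as a health index.

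Both use data already collected. The first costs a scoring step and a choice of one value set for a mixed Asia and non-Asia population, which should be made and justified while blinded. The second costs only wording in the SAP and the output shells. Section 1 already provides for a review of the SAP at the blind data review and finalisation before the blind is broken, which is the natural point for the change.
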